## 14. Study Variables

---

### 14.1 Efficacy Evaluation

The variables of the study drug PRO-087 tolerability will be evaluated in the visits indicated in the schedule, using the following parameters:

1. Best-corrected visual acuity
2. Corneal depithelization
3. Tear film break-up time

4. Schirmer test
5. OSDI
6. Goblet cells population

It is considered that the drug in evaluation PRO-087 is effective for use in patients diagnosed with mild to moderate tear film dysfunction, if they exhibit the changes marked in parameters (14.1.2) by more than 5% of subjects in both eyes, in compliance with all visits and adherence to treatment at an 80% during the time of study assessment.

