### 5.1 *MAIN OBJECTIVE:*

**To evaluate the effectiveness of preservative-free ophthalmic formulation PRO-087 (by Laboratorios Sophia, S.A. de C.V.) to restore the anatomical and physiological characteristics of the ocular surface, as well as its distribution and the characteristics of the mild to moderate tear film dysfunction syndrome compared to Systane® Ultra and Ultra Systane® preservative free (by Laboratorios Alcon, S.A. de C.V.).**

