### 7.1 *Design*

Controlled, double-blind, randomized, clinical trial comparing the safety and efficacy parameters between a group of subjects with a diagnose of mild to moderate tear film dysfunction syndrome under a regimen of ophthalmic solution lubricant drops PRO-087 versus subject under Systane® Ultra or Systane® Ultra preservative free, with the same diagnosis, with a follow-up of 90 days.

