### 13.3 Schirmer

The sample size was calculated according to the formula for continuous quantitative variables:

With a statistical confidence level of 95%, which corresponds to the error type I, and is equal to 1.96, with a potency of 80% corresponding to the error type II, and is equal to 0.84, a standard deviation for the 1.72 mm/5 min increase in the Schirmer test, with an expected difference of at least 0.13 mm/5 min, was considered.

Based on the above, the result was 80 patients, which increased 20% in consideration of the losses, with a total of 96 patients per group, with total study population of 288 subjects (576 eyes).

Based on the above calculations and considering the primary outcome variable, and Schirmer test used in the study to demonstrate efficacy between the 3 groups, the total population to evaluate will be of 288 subjects.

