#### 14.1.2 Efficacy Assessment Parameters

Parameters	Value
Best-corrected visual acuity	Increase of 1 line in the Snellen chart or 1 logarithmic point (logMAR)
Corneal depithelization	Percentage of the damaged epithelium of the ocular surface, reduction of staining according to the oxford scale.
Tear film break-up time	Increase in the residence of the teal film, measured in seconds. Increase of 30% from baseline or equal or more than 10 sec.
Schirmer test	Increase of more than 30%
Adverse events	Presence of adverse events modifying some of the abovementioned criteria or others, evaluated as serious.
OSDI	Reduction of 20% of the total score from the baseline score.
Goblet cells population	Increase of 20% from baseline

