#### 14.2 Tolerability Evaluation

Tolerability variables of the study drug PRO-087 will be evaluated in the visits indicated in the schedule, using the following parameters:

1. Burning
2. Foreign body sensation

3. Tearing
4. Conjunctival hyperemia
5. Pruritus
6. Photophobia
7. Tear secretion

It is considered that the drug in evaluation PRO-087 is tolerable for use in human beings, if there are no changes on the marked parameters (14.1.2) by more than 5% of subjects, in both eyes, in compliance with all visits and adherence to treatment at an  $\geq 80\%$  during the time of study assessment.

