## 15. Proposed statistical analysis.

---

The statistical analysis will be performed by an investigator blinded to the intervention groups.

The continuous quantitative variables will be presented by measures of central tendency and dispersion (mean, standard deviation and ranges). Nominal and ordinal qualitative variables will be introduced by means of frequencies and ratios.

The Kolmogorov-Smirnov test will be performed to know the normal or abnormal distribution of the results obtained in each study group.

Assuming there is a normal distribution of data, the intra-group differences will be determined by an ANOVA test for repeated measures, with the Pearson correlation coefficient, for the quantitative variables.

For qualitative variables the  $\chi^2$  (chi square) test will be used and in case the expected frequencies are less than 5 the Fisher's exact test will be used.

The differences between groups will be analyzed using the ANOVA test for variance analysis, with the Pearson correlation coefficient, for the qualitative variables.

For qualitative variables, contingency tables 2x2 will be used and the differences will be calculated with  $\chi^2$  (chi square) with Yates's correction and in case the expected frequencies are less than 5 the Fisher's exact test will be used.

The significance level will be of a 0.05 alpha value or less.

The final statistical analysis will include all the subjects that complete the visits listed in the activity chronogram.

Also, those who have been assigned with a treatment (intervention) and attend at least to 1 visit after the baseline will be included and analyzed until the moment they attended.

Those who do not attend at least 1 follow up visit will be excluded.

Those who do not complete the visits will be classified as population with intention to treat.

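### The only rule for calling PRO-087 effective (section 14.1) uses no comparator and is not linked to the between-group tests in section 15; the tolerability rule cites the efficacy table

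*Combined protocol and SAP*

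**What the plan says.** **Comparative statements.** The main objective (5.1) is effectiveness "as well as its distribution and the characteristics of the mild to moderate tear film dysfunction syndrome compared to Systane" Ultra, with and without preservative. Section 7.1 describes a randomized trial "comparing the safety and efficacy parameters between a group of subjects" on PRO-087 and subjects on either comparator. Section 13.3 fixes the total of 288 on the "Schirmer test used in the study to demonstrate efficacy between the 3 groups". Section 15 then states: "The differences between groups will be analyzed using the ANOVA test for variance analysis". It also states: "For qualitative variables, contingency tables 2x2 will be used and the differences will be calculated with" Yates-corrected chi-square, or Fisher's test when expected counts are small, at a 0.05 level.

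**Decision rules.** Section 14.1 gives the efficacy rule: PRO-087 is effective "if they exhibit the changes marked in parameters (14.1.2) by more than 5% of subjects in both eyes", among subjects who keep all visits and reach 80% adherence. Section 14.2 calls PRO-087 tolerable "if there are no changes on the marked parameters (14.1.2) by more than 5% of subjects", although the tolerability table is numbered 14.2.1. The safety rule after that table refers to 14.3.1 and also ends in the word tolerable.

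**Table rows.** The corneal row of 14.1.2 starts with the percentage of damaged epithelium and adds "reduction of staining according to the oxford scale"; the safety table 14.3.1 repeats this. The visual acuity rows of both tables set one Snellen line beside one logarithmic point (logMAR).

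**The concern.** A three-arm randomized trial has a stated verdict that uses one arm. Section 15 compares the groups but never mentions the 14.1.2 criteria or the 5% threshold, and does not say how a test result leads to a conclusion about efficacy. The sponsor could follow section 14.1 exactly, report PRO-087 as effective, and leave the main objective unanswered, even with data favouring a comparator. The rule also cannot be applied as it stands, because it does not say whether any or all parameters must be met. The faulty reference in 14.2 then gives tolerability a meaning opposed to efficacy on the same parameters.

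**Working it through.** **1. The plan's own numbers.** Section 13.3: 80 per group × 1.2 = 96, and 96 × 3 = 288. These reproduce. Over 5% means more than 4.0 of 80 or more than 4.8 of 96, so at least 5 responders in either case.

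**2. If one parameter is enough: a counterexample.** PRO-087 has 5/80 (6.3%), so the rule is met. A comparator has 15/80 (18.8%). Yates chi-square = N(|ad − bc| − N/2)² / (product of the four margins), with a = 5, b = 75, c = 15, d = 65, N = 160:

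- |5×65 − 75×15| = 800, and 800 − 80 = 720
- 160 × 720² / (80 × 80 × 20 × 140) = 82,944,000 / 17,920,000 = 4.63, p = 0.031

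The smallest expected count is 10, so Fisher's test is not called for. With 14/80 in the comparator p = 0.051, so 15 is the smallest such count. At 96 per group, 5 against 15 gives chi-square 4.52, p = 0.033. The counts need no assumed rates, but applying this test to the responders is my choice.

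**3. Probability that the rule passes.** P(X ≥ 5), X binomial(n, p). The documents give no responder rates, so every p is assumed.

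| p | n = 80 | n = 96 |
|---|---|---|
| 1% | 0.001 | 0.003 |
| 3% | 0.09 | 0.16 |
| 8% | 0.78 | 0.89 |
| 10% | 0.91 | 0.97 |
| 15% | 0.995 | 0.999 |

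Rates of 8% or more illustrate a single parameter. Rates of 1–3% illustrate a subject having to meet every parameter. Comparator results enter neither.

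**4. OSDI with no true change.** The criterion is a 20% fall from baseline (14.1.2). SD 6.4 (13.2) is taken as the SD of a normally distributed change with mean zero. Section 12.1 admits scores below 30.

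- Baseline 30: a fall of 6.0 is needed; 6.0/6.4 = 0.94; chance response 17.4%; P(X ≥ 5 of 80) = 0.999
- Baseline 15: a fall of 3.0 is needed; 3.0/6.4 = 0.47; chance response 32.0%; P above 0.999

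OSDI is one score per subject, so the both-eyes condition gives no protection. I give no such figure for Schirmer or TBUT, which are read eye by eye: it would depend on a between-eye correlation that the documents do not state.

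**5. Tolerability read literally.** Efficacy on a 14.1.2 parameter needs more than 5% of subjects with the change. Tolerability under 14.2 needs no more than 5% with changes in the same table. No parameter can satisfy both.

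**6. Smaller wording faults.**

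- Visual acuity: the conversion table in 10.3.2 moves 0.1 logMAR per row and 20/20 is 0.0, so higher logMAR is worse vision. An increase therefore means a gain in lines but a loss in logMAR. The safety row gives no direction.
- Corneal row of 14.3.1: it repeats the improvement wording of the efficacy table and never states worsening of staining as the harm.
- The safety rule concludes on tolerability, not safety.

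**7. Cost of a comparative rule.** Section 13.3 inputs: difference 0.13 mm, SD 1.72 mm. Two-sided t-test at 0.05: power 7.6% at 80 per group and 8.2% at 96. For 80% power, 2 × ((1.96 + 0.84) × 1.72/0.13)² = 2,745 per group. The formula printed in 13.1 has a minus sign between the two z-values; taken literally it gives 439. Neither gives 80.

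**The case against.** The strongest reply is that the comparison is planned: 13.3 ties Schirmer to efficacy between the three groups, and section 15 supplies between-group tests at 0.05. That stands. A reader might infer that the trial has no comparative analysis, but what is missing is a link from that analysis to the declaration of efficacy.

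A reader might also infer from step 2 that the plan schedules a test able to contradict its own verdict. Section 15 does not go that far. It never says that Schirmer, TBUT or OSDI will be dichotomized, and as quantitative variables they would more naturally go to ANOVA.

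Nor can the rule simply be called too lenient. The high probabilities in steps 3 and 4 hold only if one parameter is enough, and the plural in 14.1 fits an all-parameters reading equally well.

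On the smaller items:

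- One logarithmic point may mean one step of the log chart, so a demand for a full 1.0 logMAR is not proven.
- The corneal row opens with damaged epithelium, itself a harm measure, so the row is ambiguous and not shown to count healing as harm. The anterior-segment and adverse-event rows can still capture corneal harm.
- The 95%-absent cells of 14.2.1 can be reconciled with the 14.2 rule if a change means that the symptom is present.
- A missing symptom baseline cannot be asserted. The OSDI has a light-sensitivity item and is given at baseline, and the case report form is not in the documents.

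**Conclusion.** The point holds as a fault in the stated decision rules. The efficacy rule is single-arm, undefined as to any or all parameters, and unconnected to section 15, so it does not support the comparative conclusion the objective asks for on either reading. If one parameter suffices, 5/80 passes against a comparator's 15/80, and OSDI passes by chance with probability about 0.999 under the assumptions in step 4. If all are required, passing has probability 0.001–0.09 at 80 per group for an assumed composite rate of 1–3%.

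The wrong table number in 14.2 is probably a slip, but its literal effect is serious. These two faults carry the need for correction. The visual acuity, corneal and safety wording needs clarifying and would not carry the point alone. The sample-size failure in step 7 is a separate defect on which this conclusion does not depend.

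**What to change.** **14.1 and 15.** Base the efficacy conclusion on the between-group comparison of PRO-087 with each comparator at day 90 on the Schirmer test, or on another primary variable that the sponsor names. State:

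- the analysis unit: the subject (for example the mean of both eyes), or a model that accounts for paired eyes
- the analysis population, since 14.1 restricts to compliant subjects and section 15 does not
- whether the aim is superiority, which the section 13 formula only implies
- whether both comparators must be beaten (each at 0.05, no adjustment) or either (Holm)

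Report the percentage meeting each 14.1.2 criterion per arm descriptively, with differences and 95% confidence intervals.

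**14.2.** Replace the reference to 14.1.2 by 14.2.1. Say whether symptoms present at entry count, using existing baseline records, including the OSDI light-sensitivity item for photophobia.

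**14.1.2 and 14.3.1.** Write one line as 0.1 logMAR with the direction: a gain is a decrease, a loss an increase. Reconcile the 14.3.1 corneal row so that worsening of staining is the harm, with the threshold set by the sponsor. Let the safety rule conclude on safety.

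**Cost.** Amendment text and no new visits. The efficacy claim becomes harder to reach: at about 8% power on 13.3's own inputs, the stated 80% must be corrected separately.

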#### 14.1.2 Efficacy Assessment Parameters

Parameters	Value
Best-corrected visual acuity	Increase of 1 line in the Snellen chart or 1 logarithmic point (logMAR)
Corneal depithelization	Percentage of the damaged epithelium of the ocular surface, reduction of staining according to the oxford scale.
Tear film break-up time	Increase in the residence of the teal film, measured in seconds. Increase of 30% from baseline or equal or more than 10 sec.
Schirmer test	Increase of more than 30%
Adverse events	Presence of adverse events modifying some of the abovementioned criteria or others, evaluated as serious.
OSDI	Reduction of 20% of the total score from the baseline score.
Goblet cells population	Increase of 20% from baseline

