#### 14.2.1 Tolerability Parameters

Parameters	Value
Burning	It should be recorded as absent on 95% of the evaluated subjects
Foreign body sensation	It should be recorded as absent on 95% of the evaluated subjects
Tearing	It should be recorded as absent on 95% of the evaluated subjects
Secretion	It should be recorded as absent on 95% of the evaluated subjects
Conjunctival hyperemia	
The following must be accomplished:
 
 
• Absent: <math>\geq 95.0\%</math>
 
• Mild: <math>\leq 5.0\%</math>
 
• Moderate: <math>\leq 2.5\%</math>
 
• Serious: <math>\leq 1.0\%</math>
 

Photophobia	
The following must be accomplished:
 
 
• Absent: <math>\geq 95.0\%</math>
 
• Mild: <math>\leq 5.0\%</math>
 
• Moderate: <math>\leq 2.5\%</math>
 
• Serious: <math>\leq 1.0\%</math>
 

Safety variables of the study drug PRO-087 will be evaluated in the visits indicated in the schedule, using the following parameters:

1. Best-corrected visual acuity
2. Intraocular pressure
3. Ocular surface
4. Anterior segment exploration
5. Posterior segment exploration
6. Tear film break-up time
7. Schirmer test
8. Corneal depithelization
9. Adverse events

It is considered that the drug in evaluation PRO-087 is tolerable for use in human beings, if there are not changes on the marked parameters (14.3.1) by more than 5% of subjects, in both eyes, in compliance with all visits and adherence to treatment at an  $\geq 80\%$  during the time of study assessment.

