#### 14.3.1 Safety Parameters

Parameters	Value
Best-corrected visual acuity	No change of 1 line in the Snellen chart or 1 logarithmic point (logMAR)
Intraocular pressure	Measurements below 7 mmHg and over 21 mmHg
Corneal depithelization	Percentage of the damaged epithelium of the ocular surface, reduction of staining according to the Oxford scale.
Anterior segment examination	Abnormalities on any of the comprised structures: Cornea, iris, pupil, iris-corneal angle and crystalline.
Posterior segment examination	Abnormalities on any of the comprised structures: Vitreous, retina, macula and optic nerve.
Tear film break-up time	Reduction of more than 20% over the baseline time.
Schirmer test	Reduction of more than 20%
Adverse events	Presence of adverse events modifying some of the abovementioned criteria or others evaluated as serious.
OSDI	Increase of the score of more than 10 points.

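### Efficacy table 14.1.2 contains an adverse-events row, so the plan's only explicit effectiveness rule counts the presence of such events toward PRO-087 being effective

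*Combined protocol and SAP*

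**What the plan says.** Section 14.1 names six efficacy variables: best-corrected visual acuity, corneal de-epithelialization, tear break-up time (TBUT), Schirmer test, OSDI and goblet cells. It then gives the decision rule. PRO-087 is effective for the target population "if they exhibit the changes marked in parameters (14.1.2) by more than 5% of subjects in both eyes", with attendance at every visit and 80% adherence.

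Table 14.1.2, to which that rule points, has seven rows. Six correspond to the list. The seventh is adverse events, and its entry is "Presence of adverse events modifying some of the abovementioned criteria or others, evaluated as serious".

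The safety list that precedes table 14.3.1 includes "9. Adverse events". Table 14.3.1 gives the matching entry as "Presence of adverse events modifying some of the abovementioned criteria or others evaluated as serious", which differs from the efficacy entry by one comma. The rule attached to that table requires that its changes not occur in more than 5% of subjects.

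Section 14.2 has a further rule. It calls PRO-087 tolerable "if there are no changes on the marked parameters (14.1.2) by more than 5% of subjects", so it cites the efficacy table, although the tolerability parameters are in table 14.2.1.

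Section 15 plans between-group testing: "The differences between groups will be analyzed using the ANOVA test for variance analysis" and "The significance level will be of a 0.05 alpha value or less". It does not say what result would establish efficacy.

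**The concern.** A row that records harm sits inside the criterion for benefit. The other six rows describe an improvement or the measure of one: better acuity, less staining, longer TBUT, more Schirmer wetting, lower OSDI, more goblet cells. This row marks the presence of events, and the rule counts subjects who exhibit what is marked. The same event in the same subject, at the same 5% cut-off, then supports one verdict and counts against another.

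At stake is whether the effectiveness statement can be applied without a judgement made during analysis. An analyst would have to drop the row, reverse it, or treat it as a veto. The protocol authorizes none of these, and the choice could affect the answer. If it were made after data had been seen, it would be open to challenge.

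**Working it through.** The plan states no figure for this point, so there is none to reproduce. The check is a comparison of text plus the count implied by the 5% cut-off.

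**1. List against table.** The 14.1 list has 6 items and table 14.1.2 has 7 rows. The surplus row is adverse events.

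**2. Efficacy table against safety table.** The two adverse-event entries match apart from a comma. In 14.1.2, occurrence in more than 5% of subjects counts toward effective. In 14.3.1, occurrence in more than 5% counts against the product.

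**3. Is there another effectiveness criterion?** Section 13.3 names Schirmer as the variable for showing efficacy between the three groups, without a decision rule. Section 15 gives tests and an alpha, without a success criterion. The 14.1 rule is the only explicit statement of when PRO-087 is effective.

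**4. Consequence under each reading.** Section 14.1 does not say how the rows combine.
- *Any row suffices:* qualifying events in more than 5% of subjects meet the rule with no improvement anywhere. This row decides the verdict only if none of the six genuine rows passes 5%.
- *All rows required:* a product with qualifying events in 5% or fewer cannot be called effective, whatever TBUT, Schirmer or OSDI show.
- *Each parameter judged separately:* the other six verdicts stand, and only the adverse-events verdict is perverse.

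**5. Threshold count.** Section 13.3 gives 80 per group before the loss allowance and, after it, the size is stated as "with a total of 96 patients per group, with total study population of 288 subjects (576 eyes". The smallest count above 5% is:
- n = 96: 4/96 = 4.2% (no); 5/96 = 5.2% (yes)
- n = 80: 4/80 = 5.0%, which is not more than 5% (no); 5/80 = 6.25% (yes)
- n = 79: 4/79 = 5.06% (yes)

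The rule's attendance and adherence conditions may shrink the denominator, so the count is 5 for 80 or 96 evaluable subjects and 4 just below 80.

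**6. Direction of the rule (illustration).** The documents give no rate of qualifying events, so the true rate p is an assumption. With n = 96, and setting aside the both-eyes, visit and adherence conditions, the chance that the row is met is P(X ≥ 5) = 1 − Σ (k = 0 to 4) C(96,k) p^k (1−p)^(96−k).

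| Assumed p | P(row met) |
|---|---|
| 1% | 0.003 |
| 2% | 0.044 |
| 3% | 0.162 |
| 5% | 0.527 |
| 8% | 0.891 |
| 10% | 0.969 |

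The more harm there is, the more likely the efficacy row is met. The finding does not depend on these values.

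**The case against.** The strongest reply is that this is an editing slip. The 14.1 list omits adverse events, the safety list includes them, and the safety table carries almost the same sentence, so the row was very probably copied across. Nobody meant to count harm as benefit. I accept that as the likely origin. It does not remove the defect, because the row stands inside a formal decision rule and nothing written corrects it.

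Three other points also limit the finding.
- **The comparative analysis is separate.** The main objective is comparative, and the between-group tests in section 15 do not use table 14.1.2. A reader might infer that the trial's efficacy results are invalid. The documents do not support that; the effect is confined to the 14.1 effectiveness statement.
- **The rule has conditions.** A reader might infer that any five subjects with serious events would make PRO-087 effective. Section 14.1 also requires the change in both eyes, all visits and 80% adherence. Section 18.1.1 provides for the drug to be interrupted after a serious event deriving from it, so some affected subjects may fail the adherence condition and not count. The both-eyes condition also has no clear meaning for a non-ocular event.
- **The row is not limited to serious adverse events.** It covers events that modify the listed criteria, or others judged serious. That last phrase could refer to the seriousness category in 18.2.1 or to the severity grade in 18.2.2.

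**Conclusion.** The point holds as an error in the decision rule as written: the presence of adverse events of the kind described counts toward effectiveness. How far this reaches depends on the unstated way of combining rows. It can settle the verdict under the any-row reading, block it under the all-rows reading, and affects one parameter only under the separate reading. It would be too strong to say that the efficacy verdict is wrong on every reading, since the separate reading leaves the other six parameters intact.

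The size is a threshold of about 5 subjects in the PRO-087 group, possibly 4, among those who meet the rule's other conditions. This assumes the rule is applied to that group alone, with between 79 and 96 evaluable subjects. It is a threshold and not a prediction, because no event rate is given. The correction is simple, but it belongs in the protocol before the effectiveness rule is applied to data.

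**What to change.** Delete the adverse-events row from table 14.1.2, so that its six rows match the six variables in 14.1. Keep the row in table 14.3.1, so that adverse events are still judged under safety.

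In the same amendment, reconcile the tolerability rule in 14.2 with its own parameter table, 14.2.1. If the row is deleted and that reference is left alone, the six improvement rows would still count for effective under 14.1 and against tolerable under 14.2. The sentence that introduces the 14.1 list also calls those variables tolerability variables and should be corrected. State as well whether the 14.1 rule needs any row, all rows, or a separate verdict per parameter.

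The cost is one table row and a few sentences. Data collection, sample size and alpha do not change.

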Alvez M. et al. evidences that the best proof combination to achieve the greatest sensitivity, conjugating its results was to perform an OSDI, a fluorescein TBUT and a Schirmer test, which gives a combined sensitivity of 100% (95% IC 97.5 – 100), a specificity of 95% (95 IC 75.1 – 99.9%) and precision of 99.3% (95% IC 96 – 99.9). Previous findings enforce the importance of the most commonly tests used by costs, accessibility and reproducibility.

This concludes that though tear film dysfunction diagnosis algorithms are not established, basic elements to perform it are as follows:

- ❖ TBUT < 10 seconds
- ❖ Schirmer test less than 100 mm (5 minutes)
- ❖ OSDI score > 20 and < 30
- ❖ Fluorescein or rose Bengal corneal staining score  $\geq$  I (Oxford scale)
- ❖ Osmolarity > 310 mOsm

Any previous marker, added to each subject clinical chart, established the tear film dysfunction syndrome diagnosis.

Charts with OSDI > 30, a score equal or > to III on an Oxford scale with fluorescein staining and altered tear film break-up time are considered as serious.

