### 12.1 Inclusion Criteria

---

- ❖  $\geq 18$  to  $\leq 90$  years old
- ❖ Both sexes
- ❖ Mild to moderate tear film dysfunction clinical diagnose
- ❖ Mild to moderate clinical stage of the disease
  - TBUT  $> 5$  sec. and  $< 10$  sec.
  - Schirmer:  $> 4$  mm and  $< 14$  mm
  - OSDI  $< 30$  points
  - Corneal staining  $<$  grade III on the Oxford scale
- ❖ Availability to go to each revision when indicated.

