### 12.2.2 *Criteria related with ophthalmic ailments*

1. Serious tear film dysfunction syndrome
  - TBUT < 5 s
  - Schirmer: < 4 mm

- OSDI > 30 points
  - Corneal staining > grade III on the Oxford scale
2. Non perforated corneal ulcer
  3. Perforated corneal ulcer
  4. Autoimmune corneal ulcer
  5. Ocular surface scarring diseases
  6. Ocular surface or annexes metaplastic lesions
  7. Fibro vascular proliferation lesions on the conjunctival and/or corneal surface (i.e.: pterygium)
  8. Concomitant chronic inflammatory diseases on any ocular structure
  9. Acute or infectious inflammatory disease
  10. Corneal disease potentially requiring a treatment during the following 3 months
  11. Use of topical or systemic drug products classified as forbidden
  12. Ocular surgical procedures 3 months before the protocol inclusion
  13. Treatments or procedures indicated on the tear film dysfunction treatment, as punctal silicone plugs.
  14. Posterior segment diseases requiring a treatment or threatening the visual prognosis
  15. Retinal diseases potentially requiring treatment during the following 3 months
  16. History of penetrating keratoplasty.
  17. Soft or hard contact lenses use during the last month from inclusion day

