Answer the following questions by circling the box which best represents your answer:

1. Have you experienced any of the following during last week?

	FREQUENCY				
	All of the time	Most of the time	50% of the time	Some of the time	None of the time.
Eyes that are sensitive to light.	4	3	2	1	0
Eyes that feel gritty.	4	3	2	1	0
Painful or sore eyes.	4	3	2	1	0
Blurred vision.	4	3	2	1	0
Poor vision.	4	3	2	1	0
Subtotal:					

2. Have problems with your eyes limited you in performing any of the following during last week?

	FREQUENCY				
	All of the time	Most of the time	50% of the time	Some of the time	None of the time.
Reading.	4	3	2	1	0
Driving at night	4	3	2	1	0
Working with a computer or bank machine (ATM)	4	3	2	1	0
Watching TV	4	3	2	1	0
Subtotal:					

3. Have your eyes felt uncomfortable in any of the following situations during last week?

	FREQUENCY				
	All of the time	Most of the time	50% of the time	Some of the time	None of the time.
Windy conditions.	4	3	2	1	0
Places or areas with low humidity (very dry).	4	3	2	1	0
Areas that are air conditioned.	4	3	2	1	0
Subtotal:					

OSDI score= total score × 25 / number of answered questions

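### The OSDI efficacy criterion is a 20% fall with no minimum change in points, so a baseline of 0 cannot respond and one step on one question is enough at baselines up to 10.42

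*Combined protocol and SAP*

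**What the plan says.** - **Criterion.** Section 14.1.2 gives the OSDI effect as "Reduction of 20% of the total score from the baseline score". No minimum change in points is attached.
- **Use of the criterion.** Section 14.1 calls PRO-087 effective "if they exhibit the changes marked in parameters (14.1.2) by more than 5% of subjects in both eyes", among subjects who attend all visits and reach 80% adherence. The rule refers to PRO-087 subjects only and makes no comparison with either comparator.
- **Entry.** Section 12.1 asks for "OSDI $< 30$ points", while TBUT and Schirmer there have both a lower and an upper limit. Section 12.2.2 excludes "OSDI > 30 points". Neither section sets a lower OSDI limit.
- **Diagnosis.** Section 3.1 lists "OSDI score > 20 and < 30" among five diagnostic elements and adds: "Any previous marker, added to each subject clinical chart, established the tear film dysfunction syndrome diagnosis". The OSDI range is therefore one route to the diagnosis among several.
- **Scoring.** The OSDI appendix has 12 questions, each scored 0 to 4, with "OSDI score= total score × 25 / number of answered questions".
- **Sizing and analysis.** Section 13.2 sizes OSDI on a 6.1-point difference with a standard deviation of 6.4. Section 15 plans repeated-measures ANOVA within groups and ANOVA between groups. It names no OSDI endpoint, visit or baseline covariate, and has no rule for a zero or very low baseline.

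**The concern.** The change in points that counts as a response depends on where the subject starts. At 0 there is nothing to reduce. At low scores the smallest change the questionnaire can register already meets the criterion. Near the entry ceiling the required change is about the size of the planning difference.

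Low scores are foreseeable. A subject can enter on TBUT, Schirmer and staining with few symptoms, and section 3.1 itself remarks that mild to moderate disease may not be fully noticed by the patient.

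At stake is the efficacy statement for symptoms. The 5% rule in section 14.1 has no control group. A handful of low-baseline subjects who each tick one box lower at day 90 would count towards effectiveness, with nothing to set that against.

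**Working it through.** **The plan's own OSDI figure.** Section 13.2 states 34 patients before losses, raised to 41 per group and 123 in total. The standard two-group formula gives n = 2 × [(1.96 + 0.84) × 6.4 / 6.1]² = 2 × 2.938² = 17.26, so 18 per group. The figure 34 matches only the total for two groups, 4 × 2.938² = 34.5. The loss step reproduces: 34 × 1.2 = 40.8, rounded to 41, and 41 × 3 = 123. This is a separate matter. Only the 6.1 points are used below, as a yardstick.

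**Size of one step.** Let S be the sum of the item scores and k the number of questions answered. The score is S × 25 / k. With k = 12, one step on one question is 25/12 = 2.08 points.

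**Steps needed for a 20% fall.** One step lowers the score by a fraction 1/S, so the criterion needs S/5 steps, rounded up. A score below 30 with 12 answers means S ≤ 14, since 14 × 25/12 = 29.17 and 15 × 25/12 = 31.25.

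| Sum S | Baseline score | One step as % fall | Steps needed | Points needed |
|---|---|---|---|---|
| 0 | 0 | not defined | impossible | – |
| 1 to 5 | 2.08 to 10.42 | 100% to 20% | 1 | 2.08 |
| 6 to 10 | 12.5 to 20.83 | 16.7% to 10% | 2 | 4.17 |
| 11 to 14 | 22.92 to 29.17 | 9.1% to 7.1% | 3 | 6.25 |

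At S = 5 one step is a fall of exactly 20%, which meets the rule as worded. At S = 0, a program that coded the rule as follow-up ≤ 0.8 × baseline would count an unchanged 0 as a response, so the rule breaks down at 0 under either coding.

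**Against the plan's other OSDI figures.** One step is 2.08/6.1 = 34% of the planning difference. The safety criterion in section 14.3.1 is a rise of more than 10 points, which takes five steps (5 × 2.08 = 10.42). At a baseline of 10.42, improvement is therefore declared after one step and worsening after five.

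**Skipped questions.** The one-step zone always ends at S = 5, a score of 125/k: 12.5 with 10 answers, 15.6 with 8 and 20.8 with 6.

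**How few responders suffice.** With 96 subjects in the PRO-087 group (section 13.3), 5% is 0.05 × 96 = 4.8, so five responders exceed it. With 80, the number before the loss allowance, 5% is 4, and again five exceed it.

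**The case against.** Four objections carry weight.

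1. **A points analysis is already implied.** Section 13.2 sizes OSDI in points, and section 15 plans ANOVA for quantitative variables (its between-group sentence says qualitative, apparently a slip). This stands: the 20% rule need not be the only OSDI analysis. But section 15 does not name OSDI, fix day 90 or adjust for baseline, and section 14.1 still ties effectiveness to the percentage criterion.

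2. **Randomisation protects a comparison of arms.** A reader might infer that 20% responder rates can say nothing about PRO-087. The documents do not support that. Baseline mix and noise are balanced across arms in expectation, and section 15 provides chi-square or Fisher tests. Chance responders would dilute a between-arm comparison without making it uninformative. The harm lies in the uncontrolled 5% rule.

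3. **Low-OSDI subjects belong in the trial.** A reader might take above 20 and below 30 as the protocol's definition of the disease, and so treat low scorers as wrongly enrolled or limit the responder table to baselines above 20. Section 3.1 makes that range one of several alternative markers, so neither step follows. The restriction would not cure the 5% rule either, because that rule would still lack a control.

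4. **Chance response rates are not established.** One might treat change as normal with mean 0 and SD 6.4 and quote 44% chance responders at baseline 5 and 18% at 29. Section 13.2 does not say that 6.4 is the SD of within-subject change at every baseline, and OSDI cannot fall below 0. At baseline 5 that model puts about 22% of its probability below zero, so about half of the 44% is impossible scores. These rates should not be relied on.

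It is also true that any percentage criterion asks for different absolute changes at different baselines. What is specific here is the coarse scale combined with entry down to 0.

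**Conclusion.** The concern holds in a limited form. By the protocol's own scoring, the OSDI criterion cannot be met at 0, is met by the smallest recordable change at baselines 2.08 to 10.42, and needs three times that change at 22.92 to 29.17. The step counts assume only that all 12 questions are answered at both visits; the skipped-question figures assume the same number answered at both.

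The consequence rests on the 5% rule in section 14.1, read as applying to OSDI on its own. The section does not say whether the changes in 14.1.2 are judged one at a time or jointly. On a joint reading OSDI alone could not carry the claim, but subjects would still be misclassified on it.

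The share of subjects at 0 or in the one-step range cannot be stated, because the documents give no baseline OSDI distribution. OSDI is one of six efficacy variables, so this weakens the symptom claim and does not decide the whole trial.

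**What to change.** In sections 14.1.2 and 15:

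- Make the OSDI efficacy test the between-arm difference in change in points from baseline to day 90, adjusted for baseline OSDI (ANCOVA), for PRO-087 against each comparator. This replaces the unadjusted ANOVA for OSDI and agrees with the points-based sizing in section 13.2.
- Keep the 20% responder rate as a secondary descriptive table by arm, and do not use it to declare effectiveness.
- In that table, report subjects with baseline 0 separately as unable to respond, and show results for baselines up to 10.42 and above it.

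The cost is plan wording and a little more analysis work. OSDI is already collected at baseline and day 90 (section 9), so eligibility, visits and data collection do not change. One limit remains: a subject who starts below 6.1 cannot fall by 6.1 points, so many low baselines would shrink the difference between arms. The split by baseline would show this.
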